Focus group and Delphi	To elicit comments on the model stage-matched intervention.	Parent caregivers will be engaged in focus groups to give their opinions on the model intervention developed from integrated information from earlier stages. Professionals	Delphi will be e-Delphi, and focus groups will be at participating tertiary care facilities.	As with the first interview, transcription and content analysis of discussions will be done. Expert opinion will be analysed using two indicators: the degree of concentration and coordination

		(psychologists, oncologists, nurses) will give feedback through the Delphi process.		of experts' opinions.
Pilot RCT of Draft Intervention	To test the stage-matched psychological adaptation intervention for parent caregivers of children with leukemia in Pakistan.	A stage-matched intervention lasting 12 weeks with assessments conducted at baseline, mid-intervention, and end of intervention. 34 parent caregivers from each of the two study facilities (total N = 68).	A tertiary care hospital in Pakistan	Qualitative data will be transcribed and analysed. Two-tailed t-tests will be run for parametric quantitative data using 95% confidence intervals. Hedges' g formula, will be used to calculate effect sizes. Feasibility and acceptance will be measured by participants' ratings of the intervention's overall helpfulness. Baseline, midway, and post-intervention psychological adaptation and distress outcomes assessments will inform the program's initial efficacy.

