2.10 Stage 4: Pilot Trial of the Stage-Matched Intervention Draft

The last stage of the program involves testing the stage-matched psychological adaptation intervention with a population representing the participants expected to participate in a large-scale randomised controlled trial if the pilot trial produces positive productive result results. This stage is only described briefly; although the detailed procedure will be described in a protocol for the pilot trial.

Objective: The pilot trial aims to:

1. Evaluate the feasibility of the stage-matched psychological adaptation intervention among parent caregivers of children with leukemia and the acceptability of the intervention by participants.
2. Preliminarily investigate the efficacy of the intervention in improving psychological adaptation, coping, and reducing distress in parent caregivers.
3. Examine the acceptability of the stage-matched psychological adaptation intervention among parent caregivers of children with leukemia.

Method: This study will use a two-arm pilot randomized controlled trial design involving parent caregivers of children with leukemia in two facilities of a tertiary care hospital in Pakistan. To simplify implementation and minimize contamination, each facility will be randomly assigned to either the intervention or control group.

The intervention group will receive stage-matched psychological adaptation program alongside routine medical care, while the control group will continue with standard routine medical care. Cluster randomization at the facility level is employed to prevent potential spillover effects that could occur with individual randomization within the same setting. This approach reflects real-world practice, where interventions are typically implemented at the organizational level across entire facilities rather than targeting individual participants. Using cluster randomization also enhances intervention fidelity by allowing consistent delivery and standardized staff training within each facility. Moreover, it aligns the study design with practical implementation

conditions by accounting for variations in resources, workflows, and procedures across different facilities.

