Participants: Parent caregivers (biological parents or step-parents of children diagnosed with leukemia. Participants who plan to relocate outside the study area during the study period will be excluded. The sample size estimation was initially derived using individual-level power calculations.

Sample size: The sample size was selected to (1) provide precise estimates of key feasibility parameters (e.g., recruitment rate, retention, adherence), (2) align with published pilot trial recommendations (Ying et al., 2025), and (3) reflect sample sizes used in comparable psychosocial intervention pilots in pediatric oncology settings (Koyu and Kilcarslan, 2024). We aim to recruit $N = 70$ parent caregivers (35 per arm). This sample size allows estimation of a 75% retention rate with a 95% confidence interval width of $\pm 13\%$. Accounting for an anticipated 25% attrition rate common in LMIC psychosocial trials, we will recruit up to 88 participants. This sample is sufficient to assess feasibility, acceptability, and preliminary effects, while informing sample size calculations for a future definitive RCT.

Setting: The study will be conducted in a tertiary care hospital in Pakistan providing pediatric oncology services.

Study procedures: The study will be conducted over 12 weeks, with interventions delivered by trained mental health professionals and outcome assessments carried out by research assistants. After recruitment, participants will provide informed consent and be screened for eligibility. Caregivers in the intervention group will receive a stage-matched psychological adaptation program based on the transactional family adaptation model and culturally adapted coping strategies. The final intervention protocol will be developed after the initial three stages.

Outcome evaluations will be conducted at baseline, mid-intervention, and post-intervention to assess feasibility, acceptability, adherence, and effectiveness, using methods such as diaries, observations, and satisfaction measures. At the end of the study, caregivers will participate in semi-structured interviews and complete questionnaires to evaluate outcomes. Additionally, professionals delivering the intervention will be interviewed to identify strengths of the trial and assessment methods. Key outcomes include improved psychological adaptation, reduced distress,

enhanced coping skills, and better quality of life among caregivers. Figure 4 summarizes the whole procedure for the pilot RCT.

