Sustainability depends on the development of capacity. Hospital staff will be trained to deliver the intervention, a strategy shown to maintain fidelity even after the trial ends. Additionally, feasibility and acceptability data from the pilot will directly inform implementation planning for policymakers and administrators, focusing on the adoption and maintenance dimensions of RE-AIM.

Limitations

This pilot will be conducted within a single tertiary hospital, potentially limiting applicability to urban, well-resourced settings. Future research should involve multiple centers, including rural and underserved areas, where childhood cancer cases are diagnosed later and mental health resources are scarce. The study's reliance on self-reported measures may introduce social desirability bias, so integrating clinician-rated or observational assessments is recommended. The 12-week follow-up is insufficient for assessing long-term effects, so extended evaluations are needed. While culturally adaptable, further contextual adjustments may be required for specific subpopulations. Additionally, the pilot's small sample size limits statistical power; thus, a larger, multi-site trial is necessary to confirm efficacy. Lastly, excluding parents of children in the acute illness phase means findings may not reflect the highest-stress periods of the cancer journey. Additionally, the pilot RCT design with only two clusters (one intervention, one control facility) limits the statistical power for definitive hypothesis testing; therefore, the primary goal of this pilot study is to assess feasibility, acceptability, and preliminary efficacy, following CONSORT guidelines for pilot and feasibility trials (Eldridge et al., 2016). A fully powered multi-site randomized controlled trial would be required to establish definitive efficacy.

References

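### The pilot's planned t-tests leave out between-facility variance: with one facility per arm, between-arm p-values and 95% intervals are too favourable for any ICC above zero

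*Protocol*

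**What the plan says.** **Analysis.** The pilot row of Table 3 (Protocol section 2.4) names the quantitative method: "Two-tailed t-tests will be run for parametric quantitative data using 95% confidence intervals". It adds Hedges' g ("g formula, will be used to calculate effect sizes"). On use, it says "Baseline, midway, and post-intervention psychological adaptation and distress outcomes assessments will inform" the program's initial efficacy. It does not say whether the t-tests compare the two arms or compare time points within an arm.

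**Design.** In section 2.10, "each facility will be randomly assigned to either the intervention or control group", and the reason given is contamination: "Cluster randomization at the facility level is employed to prevent potential spillover effects". The Limitations confirm two clusters, one intervention facility and one control facility.

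**Sample size.** Section 2.10 aims for 70 caregivers (35 per arm) and recruits up to 88 to allow for 25% attrition. Table 3 has 34 per facility. No ICC, design effect, cluster term or cluster-level analysis appears in the Protocol.

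**Stated limitation.** The Limitations say that having only two clusters "limits the statistical power for definitive hypothesis testing", and that a fully powered multi-site trial is needed to establish efficacy.

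**The concern.** The facility is the unit of randomisation, and there is one per arm. Any difference between the two facilities in case mix, staffing or usual care is therefore inseparable from the treatment difference. A two-sample t-test on caregivers builds its standard error from the spread of caregivers within facilities only. It treats the facility difference as zero, or as part of the effect.

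At stake are the error bars on the preliminary efficacy results. An interval for adaptation or distress that excludes zero, or a p-value below 0.05, would look like a signal at the usual 5% level when the true false-positive rate is higher. The Protocol lists preliminary efficacy among the pilot's objectives (section 2.10) and plans preliminary effectiveness reports for external dissemination (section 2.13). The stated limitation would not warn a reader, because limited power suggests missed effects rather than intervals that are too narrow.

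**Working it through.** The Protocol states no alpha, power or effect size for the t-tests, so there is no figure of its own to reproduce on this point. A two-sided 5% level is implied by the two-tailed tests and 95% intervals.

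**Step 1: which test is possible.** A t-test on facility means has 2 − 2 = 0 degrees of freedom, so it cannot be computed. A between-arm t-test must therefore use individual caregivers. A before-after test within one arm can be computed, but it does not estimate the randomised effect.

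**Step 2: inputs.**
- Completers per facility: 88 × 0.75 / 2 = 33 (88 and 25% attrition from section 2.10, split equally).
- ICC: not in the Protocol. Assumed values are 0.01, 0.05 and 0.10.
- Degrees of freedom: 2(33 − 1) = 64, so t_crit = 1.998.

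**Step 3: inflation of the t statistic.** With one facility of m caregivers per arm, the variance of the difference in means is proportional to 1 + (m − 1)ICC. The pooled within-facility variance used by the t-test estimates only the fraction 1 − ICC of the total. With no treatment effect, the t statistic is therefore too large by

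k = sqrt((1 + (m − 1)ICC) / (1 − ICC)),

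and the true two-sided error rate is 2·P(t_64 > t_crit / k). Coverage of the nominal 95% interval is 1 minus that rate.

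| ICC (assumed) | 1 + 32·ICC | k | t_crit / k | True error rate | Coverage of the 95% interval |
|---|---|---|---|---|---|
| 0 | 1.00 | 1.00 | 1.998 | 5.0% | 95.0% |
| 0.01 | 1.32 | sqrt(1.32/0.99) = 1.15 | 1.730 | 8.8% | 91.2% |
| 0.05 | 2.60 | sqrt(2.60/0.95) = 1.65 | 1.208 | 23.2% | 76.8% |
| 0.10 | 4.20 | sqrt(4.20/0.90) = 2.16 | 0.925 | 35.9% | 64.1% |

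**Step 4: other cluster sizes.** With 34 per facility (Table 3), the error rates are 9.0%, 23.6% and 36.4%. With 44 per facility (88 recruited, no loss), they are 10.2%, 27.8% and 41.5%. Simulation with 100,000 replicates per scenario gave 9.0%, 23.5% and 36.3% at 34, and 10.2%, 27.9% and 41.5% at 44.

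**Step 5: interval width.** At m = 33 the t-test half-width is 1.998 × sqrt(2/33) = 0.49 within-facility SD. Multiplied by k, it becomes about 0.57, 0.81 and 1.06 SD for the three ICCs. The multiplier is a square root: 1 + (m − 1)ICC inflates the variance, not the width.

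**The case against.** The strongest reply is that this is a pilot and the Protocol knows its limits. The Limitations disclose the two clusters, disclaim definitive testing and defer efficacy to a larger trial. Section 2.10.1 bases the decision to proceed on a process evaluation, and its own analysis paragraph names no t-test. Section 2.10 says the stage is described only briefly and that a separate pilot protocol will follow. All of this stands, and it limits the consequence: no confirmatory claim or stated progression rule rests on a p-value. It does not answer the point. The method is named, and no later plan can estimate facility variance from one facility per arm; neither a random facility effect nor robust standard errors would help.

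It is also fair that the size depends on an ICC the Protocol does not give. At ICC 0 the test is nominal, and at 0.01 the inflation is modest.

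Three stronger readings are tempting but not supported:
- A reader might infer that section 2.10 claims a statistical adjustment where it describes the design as working "by accounting for variations in resources, workflows, and procedures across different facilities". In context this is a pragmatic rationale about delivering the program across organisations, and it need not be struck.
- A reader might count the sentence "The sample size estimation was initially derived using individual-level power calculations" as part of the fault. It describes how the number was derived, not whether the tests are valid, and deleting it would only reduce transparency.
- A reader might conclude that the limitation on power is backwards. It is incomplete, not wrong: a facility-level comparison with 0 degrees of freedom has no usable power. Under-coverage is a further limitation that goes unmentioned.

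**Conclusion.** The point holds for between-arm comparisons, which is an inference about what Table 3 intends, because the table does not name the contrast. If within-arm tests are meant instead, they do not provide the randomised comparison that efficacy requires. For any ICC above zero the between-arm p-values and intervals are too favourable. At 33 completers per facility and assumed ICCs of 0.01, 0.05 and 0.10, the true error rate is about 9%, 23% or 36%, and coverage about 91%, 77% or 64%. The direction does not depend on the chosen ICC, but the percentages do. The change should be made. It is not critical to the trial, because the stated goals include feasibility and acceptability, and progression rests on process evaluation.

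**What to change.** **Table 3, pilot row.** Drop the between-arm t-tests and p-values. Report mean, SD and change by facility. Show Hedges' g descriptively. If an interval is given, label it a sensitivity range and multiply the t-test half-width by sqrt((1 + (m − 1)ICC)/(1 − ICC)): about 1.15, 1.65 and 2.16 at m = 33 for assumed ICCs of 0.01, 0.05 and 0.10. If any within-arm before-after summaries are kept, say that they do not estimate the randomised effect.

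**Limitations.** Add that facility and treatment are fully confounded with one facility per arm, so no valid between-arm test of efficacy is possible.

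**Cost.** Wording only. The report will carry no between-arm p-values, and any intervals will be wider. Recruitment, assessments and the feasibility and acceptability aims are unaffected.

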2.10.1 Method of Outcome and Process Evaluation

Preliminary psychosocial outcomes (psychological adaptation, distress, coping, and quality of life) will be assessed using validated tools such as the (1) sociodemographic information, (2) Psychological Adaptation Scale (PAS)(Biesecker et al., 2013), (3) Depression Anxiety and Stress Scale (DASS-21) (Lovibond&Lovibond, 1995), (4) Caregiver burden scale(Zarit et al., 1980)., (5) Perceived Social Support Questionnaire) l(Zimet et al., 1988).The Reach, Effectiveness, Adoption, Implementation and Maintenance (RE-AIM)(Glasgow et al., 1999) framework will be utilized for implementation outcomes.Process evaluation will examine feasibility outcomes (fidelity, acceptability, participant compliance, attendance, and assignment completion records, journal entries, qualitative interviews on perceived changes, and recruitment rate). The Client Satisfaction Questionnaire (CSQ-8) will be used for acceptability, with measures such as audio recordings, direct observation, and supervision logs as fidelity monitoring procedures.

Analyses: Detailed demographic and baseline characteristics will be provided, and all findings will be systematically analysed and documented. Quantitative analysis will cover recruitment and retention rates, participants' responses to the intervention, and session frequency and duration, as measured by the Client Satisfaction Questionnaire (CSQ). Qualitative interview data will be analysed using the same approach applied in the earlier stages of the program. The preliminary findings from the pilot RCT will decide whether we will advance to a comprehensive efficacy trial. This decision will be based on a comprehensive process evaluation of the intervention components, implementation, and trial procedures. Key considerations will include participant feedback on the acceptability, feasibility, and tolerability of the intervention, as well as the relevance and practicality of the outcome measures. These criteria and decision-making processes will be clearly specified in the pilot RCT protocol.

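### Table 3 fixes a plain t-test with Hedges' g for efficacy and does not say how the baseline scores enter it; a baseline-adjusted comparison is the better choice with one facility per arm

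*Protocol*

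**What the plan says.** The efficacy analysis of the pilot is in Protocol section 2.4, Table 3, in the data-analysis column of the pilot RCT row. It states: "Two-tailed t-tests will be run for parametric quantitative data", with 95% intervals, and then "Hedges' g formula, will be used to calculate effect sizes". The same cell adds that "Baseline, midway, and post-intervention psychological adaptation and distress outcomes assessments will inform the program's initial efficacy". It does not say whether the t-test and g are computed on post-intervention scores, on change from baseline or within each arm.

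Section 2.10 (study procedures) confirms the measurement times: "Outcome evaluations will be conducted at baseline, mid-intervention, and post-intervention". The analysis paragraph of section 2.10.1 says of baseline only that "Detailed demographic and baseline characteristics will be provided", and gives no efficacy model. No covariate, analysis of covariance or change score is named anywhere in the document.

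On the design, section 2.10 says that "each facility will be randomly assigned to either the intervention or control group", and the Limitations paragraph describes "the pilot RCT design with only two clusters (one intervention, one control facility").

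**The concern.** Randomising two facilities, one to each arm, decides which facility gets the programme. It does not make the caregivers of the two facilities alike. Whatever gap in distress or adaptation exists between them is present in the trial, and recruiting more caregivers does not shrink it. The protocol gives reasons to expect a gap. Section 2.10 refers to differences between facilities in resources and ways of working. Section 2.5 admits caregivers whatever the child's stage of treatment. The Limitations paragraph says the acute phase is excluded, but several phases remain on either reading.

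The baseline scores are the one measurement that can reduce this problem, and they will be collected anyway. A t-test has no place for a covariate. It can use baseline only by subtracting it, and the plan does not say that it does.

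The effect size has a use beyond the pilot: section 2.10 says the sample will inform the sample size of the later definitive trial. A g that carries a facility gap would misinform that calculation.

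**Working it through.** **Inputs from the protocol.** Two-tailed t-test with 95% intervals and Hedges' g (Table 3); one facility per arm (section 2.10 and Limitations); 35 caregivers per arm (section 2.10, sample size). Table 3 has 34 per facility. The 88 recruits less 25% leave 66, or 33 per arm. The results barely depend on which is used: the post-score half-widths below would be 0.484 SD at 34 and 0.492 SD at 33.

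**Inputs the protocol does not give, so assumed.** Outcome SD of 1 at baseline and follow-up; ρ = 0.3, 0.5 or 0.7; a baseline gap d0 of 0.3 SD between facilities (intervention minus control); no true effect when bias is examined. The protocol states no power or precision for efficacy, so there is no figure of its own to reproduce here.

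**Precision.** The variance of one caregiver's contribution, in SD² units, is 1 for the post score, 2(1−ρ) for the change score and 1−ρ² for the baseline-adjusted score (large-sample form). The 95% half-width for a difference between arms is t(0.975; 2n−2) × √(2v/n). At n = 35 and v = 1 this is 0.477 SD.

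| ρ | Post score | Change score | Baseline-adjusted | SE cut, adjusted against post: 1−√(1−ρ²) |
|---|---|---|---|---|
| 0.3 | 0.477 | 0.564 | 0.455 | 5% |
| 0.5 | 0.477 | 0.477 | 0.413 | 13% |
| 0.7 | 0.477 | 0.369 | 0.341 | 29% |

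The change score is never better than adjustment on this formula, because 2(1−ρ) − (1−ρ²) = (1−ρ)², which is positive for any ρ below 1. It matches the post score at ρ = 0.5 and is worse below that. All these half-widths treat caregivers as independent. They ignore clustering, so they compare the methods but do not give the pilot's real precision.

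**Starting gap.** Two cases bracket what may happen to d0 by follow-up with no true effect: it regresses to ρ·d0, or it persists in full as a lasting facility difference. The expected error in the estimated difference is then:

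| Method | Gap regresses | Gap persists |
|---|---|---|
| Post score | ρ·d0 | d0 |
| Change score | −(1−ρ)·d0 | 0 |
| Baseline-adjusted | 0 | (1−ρ)·d0 |

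With d0 = 0.3 SD and ρ = 0.5:

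- Post score: 0.5 × 0.3 = 0.15 if the gap regresses, 0.30 if it persists.
- Change score: −0.15, or 0.
- Adjusted: 0, or 0.15.

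Across ρ = 0.3, 0.5 and 0.7, the post-score error under regression is 0.09, 0.15 and 0.21 SD. The adjusted error under persistence is 0.21, 0.15 and 0.09 SD.

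A simulation of 20,000 trials per setting at 35 per arm reproduced these values. With d0 = 0.3 and ρ = 0.5, the post-score t-test rejected at the two-sided 5% level in 9% of trials when the gap regressed and in 24% when it persisted, with no true effect in either case.

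**The case against.** The strongest reply is that the protocol does not say what a critic might infer from it. A reader could take a plain t-test to mean that baseline is ignored. The text does not go that far: a two-sample t-test on change scores fits the wording, and the same cell gives the baseline assessments a part in judging initial efficacy. This stands. What can be said is that no mechanism is given and that neither between-arm reading of the t-test is as good as adjustment.

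A second reply is that adjustment does not win everywhere. If the gap is a lasting facility difference, the change score removes it and adjustment leaves (1−ρ)·d0. This also stands, and the document cannot tell us which case applies. Adjustment is still preferred. Its error is no larger than the post score's in either case, it is exact if the gap regresses, and it is more precise than the change score. Showing mean changes beside it lets the reader see the other case.

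A third reply is that section 2.10 leaves the detailed procedure to a separate pilot protocol, that section 2.10.1 rests progression on process, acceptability and feasibility, and that the Limitations paragraph concedes two clusters and limited power. These points lower the weight of the concern. They do not remove it, because Table 3 already names a test and the effect size is meant to feed later planning.

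A reader might also suppose that within-arm tests would credit spontaneous improvement to the programme. The Introduction describes adaptation as changing from phase to phase, with new demands in each; it does not describe improvement over time. Section 2.10 also sets out a two-arm comparison. That reading is not supported.

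**Conclusion.** The point holds in a limited form. The plan names a t-test and Hedges' g, leaves the tested score and the role of baseline unstated, and so passes over a better method that needs no new data.

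Against a post-score test, the loss of precision is small at ρ = 0.3 (5% of the standard error) and material at 0.5 or 0.7 (13% or 29%). These figures rest on assumed correlations and ignore clustering.

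It would be too strong to say that any starting difference passes whole into the effect size. That is so only for a post-score test and a gap that persists; if the gap regresses, the share is ρ. It would also be too strong to present adjustment as a cure. Arm and facility coincide, no between-facility variance can be estimated from one facility per arm, and (1−ρ)·d0 of a lasting difference remains. The efficacy result stays descriptive under any of these methods.

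**What to change.** In the pilot RCT row of Table 3, replace the t-test for each scale with a linear model of the follow-up score on arm and the baseline value of that same scale. Report the adjusted difference with its 95% confidence interval and a standardised effect derived from it, and say which SD is the divisor. Show the unadjusted means and the mean changes by arm beside it. State that the result is descriptive because facility and arm cannot be separated. Carry the same wording into section 2.10.1 and the separate pilot protocol.

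The cost is a few lines of analysis text. No new data, visits or participants are needed.
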